**The primary analysis**

Comparing the incidence of myocardial injury (No. (%)) in the intervention group versus the control group. We plan to use a chi-square test. The difference is considered to be significant if the two-sided p-value < 0.05.

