- Number of patients with peak plasma cardiac troponin I (cTnI)  $\geq$  45ng/L (99th percentile URL, 10% CV at 40ng/L) during surgery or during the first 4 days after surgery (perioperative myocardial injury). If elevated at baseline (preoperative) a 20% or greater increase of cTnI according to baseline is required for the diagnosis of a perioperative myocardial injury [15].
  - o Holstebro Hospital: Number of patients with peak plasma cardiac troponin I (cTnI) > 24 ng/L (99th percentile URL, 14% CV)

*Secondary outcome*

- Peak plasma cTnI and total cTnI release (area under the curve) during surgery or during the first 4 days after surgery
- Plasma N-terminal Pro-Brain Natriuretic Peptide (NT-proBNP) before surgery and at day 1 after surgery.
- Endothelial dysfunction assessed by the non-invasive EndoPat system (24 hours after surgery, only done at Zealand University Hospital)
- Biomarkers of coagulation (only patients included at Holstebro Hospital)
- Perioperative myocardial infarction (Universal definition of myocardial infarction, published in 2012 [15])
  - A typical rise or fall of cTnI with peak plasma cTnI  $\geq$  45ng/L (99th percentile URL, 10% CV at 40 ng/L) (Holstebro cTnI > 24 ng/L), and with at least one of the following:
    - Symptoms of ischemia

---

 Defined as a preoperative cTnI  $\geq$  45ng/L (99th percentile URL, 10% CV at 40ng/L)

- New or presumed new significant ST-segment-T wave (ST-T) changes or new left bundle branch block (LBBB)
  - Development of pathologic Q waves in the ECG
  - Imaging evidence of new loss of viable myocardium or new regional wall motion abnormality
  - Identification of an intracoronary thrombus by angiography or autopsy
- Cardiac death with symptoms suggestive of myocardial ischemia and presumed new ischemic ECG changes or new LBBB, but death occurred before cardiac biomarkers were obtained, or before cardiac biomarker values would be increased.
  - Development of new pathologic Q waves on an ECG or pathological findings of a healing myocardial infarction if troponin levels were obtained at times that could have missed the clinical event
- Major adverse cardiovascular events (30 days, one year and five years after surgery)

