#### *Participant timeline*

*Intervention:* The remote ischemic preconditioning procedure is carried out immediately after the induction of regional or general anesthesia. The blood pressure cuff is placed on the upper limb. The cuff is inflated to 200 mmHg resulting in a total occlusion of the blood flow to the limb. After 5 minutes of ischemia the cuff is deflated and the limb is reperfused for 5 minutes. The procedure is carried out 4 times in a row. For patients with systolic blood pressures >185 mmHg, the cuff will be inflated to at least 15 mmHg above the patient's systolic blood pressure. The first round should be completed before the initiation of surgery.

The patients will have blood collected to assess cTnI (preoperative and in the morning at days 1, 2, 3 and 4 after surgery) and NT proBNP (preoperative and in the morning at day 1 after surgery). All patients with a cTnI assessment  $\geq 45\text{ng/L}$  will have a minimum of one ECG performed and a medical doctor will evaluate the patient for the presence of an ischemic or non-ischemic event that can explain the elevated cTnI (i.e. sepsis, pulmonary embolism, cardioversion). The medical doctor will determine whether further action should be taken. If necessary, a cardiologist will be consulted. Patient included at Holstebro Hospital will have blood collected for assessment of coagulation biomarkers. The blood samples are taken preoperatively, 2 hours after incision and in the morning at day 1 and 2 after surgery (4 times 6 ml blood).

The investigator observes the patients during their stay in hospital and records the occurrence of any primary or secondary outcomes. The investigator will undertake a short- and long-term follow up (30 days, one and five years after surgery) and record the occurrence of any primary or secondary outcomes. The follow-up will be carried out by reviewing the patients' electronic hospital records, by a personal phone call and with data from the Danish National Patient Register and "Dødsårsagsregisteret".

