### Plasma cardiac troponin I

Plasma cTnI will be analyzed at the local department of biochemistry using Siemens Healthcare Dimension Vista (Zealand University Hospital, Herlev Hospital), Abbott high-sensitive troponin I (Holstebro Hospital).

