**The PIXIE study**

**Statistical analysis plan for the primary publication**

**Definitions of the population**

*Intention-to-treat:* randomized in the trial and a minimum of two postoperative troponin assessments within four days of surgery (an evaluable primary outcome)

*Per-protocol:* randomized in the trial, received the allocated treatment, and a minimum of two postoperative troponin assessments within four days of surgery

We will do a per-protocol analysis and an intention-to-treat analysis.

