## **Final version**

- Total troponin I release (area under the curve) during the first four days after surgery (stratified on cardiac troponin I and high-sensitive troponin I)
- Perioperative myocardial infarction
- Major adverse cardiovascular events (30 days)
- Length of postoperative hospital stay
- Intensive care unit admission
- All-cause mortality (30 days)

To analyze the association between the intervention and the primary outcome, myocardial injury, we will do a univariate and multivariate logistic regression. The results will be expressed as odds ratios (95% confidence interval).

The decision to include a variable in the multivariate logistic regression will be based on clinical hypotheses. Trial site effect will be analyzed. A maximum of one variable per 10 primary events will be included.

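### The primary chi-square test is valid but unadjusted: preoperative troponin is not in it, and the secondary logistic model does not name it in advance

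*Combined protocol and SAP*

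**What the plan says.** - **Primary test** (SAP, final version, The primary analysis): "Comparing the incidence of myocardial injury (No. (%)) in the intervention group versus the control group. We plan to use a chi-square test", two-sided at 0.05. No covariate or stratum is mentioned. The protocol's Allocation and blinding section describes no stratified randomisation.
- **Population** (SAP, Definitions of the population): intention-to-treat patients need "a minimum of two postoperative troponin assessments within four days of surgery (an evaluable primary outcome"). No preoperative value is required.
- **Baseline measurement** (final protocol, Participant timeline): "The patients will have blood collected to assess cTnI (preoperative and in the morning at days 1, 2, 3 and 4 after surgery").
- **Use of baseline** (final protocol, Primary outcome): if the preoperative value is elevated, "a 20% or greater increase of cTnI according to baseline is required for the diagnosis of a perioperative myocardial injury". The footnote for elevated baseline ("Defined as a preoperative cTnI" of at least 45 ng/L) gives one cut-off only.
- **Assay** (final protocol, Plasma cardiac troponin I): "Siemens Healthcare Dimension Vista (Zealand University Hospital, Herlev Hospital), Abbott high-sensitive troponin I (Holstebro Hospital"). Site therefore fixes the assay, and the event cut-off changes with it: "Holstebro Hospital: Number of patients with peak plasma cardiac troponin I (cTnI) > 24 ng/L", against 45 ng/L or more at the other two sites.
- **Adjusted analysis** (SAP, final version, under the secondary analyses): a univariate and multivariate logistic regression of myocardial injury, with at most one variable per 10 events. On covariates: "The decision to include a variable in the multivariate logistic regression will be based on clinical hypotheses. Trial site effect will be analyzed".
- **Peak and total troponin** are compared separately by assay, using two-sample tests without baseline.

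**The concern.** A preoperative troponin value is a natural candidate predictor of postoperative troponin, and the trial plans to collect it anyway. Assay may also shift the event rate, because the cut-offs differ. A test that ignores both may give up some power. The open covariate list has a second consequence: several adjusted odds ratios for the primary outcome could be produced, and the plan does not say which one counts. What is at stake is a little precision and one unfixed analysis choice, not the validity of the primary result.

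**Working it through.** **Inputs from the SAP sample-size section:** 15% versus 7%, two-sided alpha 0.05, power 80%, 264 per arm calculated, 270 per arm evaluable. The interim look was dropped, so the full 0.05 applies.

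**1. Reproduce 264.** With mean rate 0.11 and difference 0.08:

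n = [1.960·√(2·0.11·0.89) + 0.842·√(0.15·0.85 + 0.07·0.93)]² / 0.08² = 238.9, so 239 per arm.

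With the continuity correction: (n/4)·[1 + √(1 + 4/(n·0.08))]² = 263.4, so 264. The plan's figure reproduces exactly, but only with the correction.

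**2. Power of the planned test at 270 per arm.**
- Uncorrected: Φ[(0.08 − 1.960·√(0.1958/270)) / √(0.1926/270)] = Φ(1.019) = 84.6%.
- Corrected (0.08 replaced by 0.08 − 1/270): Φ(0.880) = 81.1%.

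The SAP does not say which version applies.

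**3. Gain from stratifying.** Simulation used 60,000 trials per setting, unstratified 1:1 allocation, and a common within-stratum odds ratio with arm averages fixed at 15% and 7%. There are four strata (assay by elevated baseline). One third of patients on the high-sensitive assay and 15% elevated are assumptions. Both tests are uncorrected.

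| Control risk ratio: assay, elevated baseline | Chi-square | CMH | Change (points) |
|---|---|---|---|
| 1 and 1 (not prognostic) | 85.1% | 84.9% | −0.2 |
| 1.6 and 0.5 | 85.4% | 85.6% | +0.2 |
| 1.6 and 2 | 85.3% | 85.8% | +0.4 |
| 2 and 3 | 85.2% | 87.5% | +2.2 |
| 3 and 3 | 85.5% | 89.1% | +3.5 |

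Repeat runs differ by a few tenths of a point: +0.6 for 1.6 and 2, and +3.7 for 3 and 3.

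**4. Is a strong association plausible under the 20%-rise rule?** That rule makes it harder for a patient with elevated baseline to be an event, so even the direction is uncertain. Modelling the rule in 36 assumed settings gave a control risk ratio for elevated baseline from 0.38 to 6.3, below 1 in 6 settings. The gain was 0 to 5.0 points, median about 0.5, and at most 2.0 in 30 of 36. More than 2 points needed a risk ratio of about 4.

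A formula check agrees. If baseline explains a share R² of outcome variance, the effective size is 270/(1 − R²) per arm:
- R² = 0.05: 284 per arm, 86.4% (+1.8)
- R² = 0.10: 300 per arm, 88.1% (+3.5)
- R² = 0.15: 318 per arm, 89.8% (+5.2)

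**5. Details that can cancel the gain.**
- *Continuity correction.* A corrected CMH had 82.0% (1.6 and 0.5), 82.3% (1.6 and 2) and 84.2% (2 and 3), each below the uncorrected chi-square.
- *Missing baseline.* Dropping 5% of patients lowers formula power to 82.7%, and dropping 10% lowers it to 80.7%. Putting them in the not-elevated stratum costs at most 0.3 points against complete baselines.

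**6. Sparse strata.** The smallest stratum holds 540 × 1/3 × 0.15 = 27 patients, or about 5 if 20% are at Holstebro and 5% are elevated (540 × 0.20 × 0.05 = 5.4). Across the sparse settings tried, CMH type I error was 4.9% to 5.1% and confidence-interval coverage at least 94.8%.

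**7. Holstebro cut-offs side by side.** An event there needs a peak above 24 ng/L; the 20% rise applies only if baseline is elevated, and elevated means 45 ng/L or more. Read literally, a Holstebro patient stable between the two is an event with no rise. If one third of patients are at Holstebro and 5% of them are in this position (both assumed), the rates become 0.15 + 0.0167·0.85 = 16.4% and 0.07 + 0.0167·0.93 = 8.5%, and uncorrected power is 79.1%. At 10% the rates are 17.8% and 10.1%, and power is 73.8%. This is a question of endpoint definition and is not counted in the adjustment gain.

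**The case against.** The strongest reply is that nothing here is an error. Randomisation is not described as stratified, so no design feature calls for an adjusted test. An unadjusted primary test with a supportive adjusted model is a legitimate choice. That stands, and it is why the point is minor.

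The plan also covers part of the ground already. Trial site will be analysed, site determines assay, and peak and total troponin are split by assay. What is left is one unnamed covariate and an open choice of adjusted estimate.

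Three stronger readings are tempting, and the documents do not support them:
- *That baseline troponin is excluded from every model.* The covariate list is left to clinical hypotheses, so baseline troponin is neither named nor ruled out.
- *That mixing two assays and cut-offs invalidates the chi-square.* Nothing described ties assay to treatment arm, so the comparison stays fair. Simulated type I error was close to 5%.
- *That the trial has a five-point power reserve, 85% against 80% planned.* Most of that margin comes from dropping the continuity correction used to obtain 264. On the same basis, 270 per arm gives 81.1%.

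The literal reading of the Holstebro rule can also be contested. The site-specific line may replace only the threshold and leave the 20% rule to follow it. The text does not settle this.

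**Conclusion.** The point holds as a minor one. The primary chi-square is valid; preoperative troponin is outside it and is not pre-named in the secondary logistic model. Adjusting for assay and elevated baseline would change power by about −0.2 to +2 points under weak to moderate prognosis, and by up to about 4 to 5 points if baseline is strongly prognostic. No figure in that range comes from the documents: prognostic strength, Holstebro share, elevated-baseline rate and missing-baseline rate are all assumed. Two benefits do not depend on the size of the gain. Naming the adjustment fixes which adjusted estimate counts, and defining the strata forces a decision on the Holstebro baseline cut-off.

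**What to change.** Before unblinding:

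1. Prespecify a Cochran-Mantel-Haenszel test, stated to be **without continuity correction**, stratified by assay and by preoperative troponin (elevated or not), in all randomised patients with an evaluable primary outcome. Report the Mantel-Haenszel risk difference and odds ratio with 95% confidence intervals. Keep the unadjusted chi-square as a sensitivity analysis.
2. If the chi-square stays primary, name site and baseline troponin (elevated or not) as the covariates of the logistic model. Treatment, two site terms and baseline make 4 parameters. This fits the one-per-10 cap at 59 expected events (270 × 0.22), and at 43 events if the overall rate were 8% of 540.
3. For stratification only, place patients with a missing baseline in the not-elevated stratum so that none is dropped. How their events are classified is a separate endpoint rule, to be stated on its own.
4. Analyse log peak and log AUC troponin within assay, adjusted for log baseline. The residual variance of log peak falls by the factor 1 − ρ²: 0.91, 0.75 or 0.51 at assumed correlations of 0.3, 0.5 or 0.7.
5. Separately, reconcile the elevated-baseline footnote with the Holstebro event cut-off, and state the baseline cut-off for each assay.

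The cost is SAP wording, plus a clarification of the protocol footnote; no new data are needed. The downsides are about 0.1 to 0.2 points of power if the covariates are not prognostic, and some sparse strata.

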**Secondary analyses**

All analyses compare the difference between the intervention group and the control group. Continuous outcomes will be analyzed with non-parametric (Wilcoxon two-sample test) or parametric statistics (unpaired t-test) depending on data distribution and equality of variances. If necessary data will be logarithm transformed. Continuous outcomes will be expressed as mean (95% confidence interval) or median (inter-quartile range). Categorical outcomes will be analyzed with a chi-square test or Fischer's exact test (an expected count < five in one cell) and the result will be expressed as no. (%). Differences are considered significant if the two-sided p-value < 0.05.

Secondary comparisons include

- Peak plasma troponin I within four days of surgery (stratified on cardiac troponin I and high-sensitive troponin I)

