### *Statistics*

All statistical analysis will be done with SPSS/PC+ package (SSPS, Chicago, IL, USA) or the SAS 9.3 package. Data will be analyzed using non-parametric or parametric statistics depending on the distribution of data. Differences are considered significant when  $p < 0.05$ . We will do a per-protocol analysis and an intention-to-treat analysis.

A medical doctor will evaluate all patients with a rise in cTnI  $\geq 45\text{ng/L}$  in order to determine whether the elevation in cTnI is due to an ischemic or non-ischemic disease. In the final data analysis, we will do an analysis, which includes all patients (ischemic and non-ischemic) and a second analysis, which will only include patients with an ischemic disease.

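### Seven secondary comparisons are each called significant at two-sided p < 0.05, with no testing order, gate on the primary result, adjustment or exploratory label

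*Combined protocol and SAP*

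**What the plan says.** The final SAP has one primary comparison, the incidence of myocardial injury by chi-square test, with the rule "The difference is considered to be significant if the two-sided p-value < 0.05".

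Under Secondary analyses it states a second rule, "Differences are considered significant if the two-sided p-value < 0.05", and lists seven comparisons:

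1. peak troponin I
2. troponin I area under the curve (AUC)
3. perioperative myocardial infarction
4. major adverse cardiovascular events (MACE) at 30 days
5. postoperative hospital stay
6. intensive care admission
7. all-cause mortality at 30 days

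The two troponin outcomes are to be stratified by assay; the first reads "Peak plasma troponin I within four days of surgery (stratified on cardiac troponin I and high-sensitive troponin I". The SAP does not say whether that yields one combined p-value or one per stratum.

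The Statistics section of the current (multi-site) protocol sets p < 0.05 for differences in general. That protocol's secondary list also contains NT-proBNP, endothelial function, coagulation biomarkers, and MACE and mortality at one and five years. Neither document gives a testing order, a condition on the primary result, a correction or an exploratory label.

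**The concern.** This is a stated decision rule, not missing detail. Followed literally, a single secondary p-value of 0.04 is a significant difference whether or not the primary test succeeds.

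The trial is powered only for myocardial injury. The current protocol's section on the possible significance of the trial looks ahead to lower cardiovascular morbidity and mortality. Within the SAP, any support for that would have to come from secondary outcomes: infarction, MACE and death. The case the rule handles badly is a null primary result beside one favourable secondary result. The plan gives the reader no prespecified reason to treat that result as a lead rather than a finding.

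**Working it through.** **Step 1. Where the stated 5% is spent.** Inputs from the SAP's Sample size section: 15% versus 7%, type I error 5%, type II error 20%, 264 per arm.

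- Without continuity correction: n = [1.960 × √(2 × 0.11 × 0.89) + 0.842 × √(0.15 × 0.85 + 0.07 × 0.93)]² / 0.08² = (0.867 + 0.369)² / 0.0064, which rounds up to 239 per arm.
- With continuity correction: (n/4) × [1 + √(1 + 4/(0.08n))]² gives 264 per arm, the stated figure.

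So the 5% in the sample size is the two-sided level of the primary test alone. The documents state no error rate for the secondary outcomes as a family.

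**Step 2. Independent tests.** The chance of at least one p < 0.05 when nothing differs is 1 − 0.95^k.

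- k = 7, the listed comparisons: 1 − 0.95^7 = 0.302.
- k = 9, if peak and AUC are each tested in both assay strata: 1 − 0.95^9 = 0.370.
- A false result favouring the intervention, k = 7: 1 − 0.975^7 = 0.162.

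**Step 3. Correlated tests.** The outcomes are surely correlated, but the documents give no correlations, so these are assumptions. The table comes from simulated normal test statistics with a common correlation (400,000 draws per setting). It counts any |Z| > 1.96, or any Z > 1.96 for the one-direction column.

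| Assumed correlation | 7 tests, either direction | 9 tests, either direction | 7 tests, favouring intervention |
|---|---|---|---|
| 0 | 0.30 | 0.37 | 0.16 |
| 0.3 | 0.27 | 0.33 | 0.14 |
| 0.5 | 0.23 | 0.27 | 0.11 to 0.12 |
| 0.7 | 0.18 | 0.20 | 0.09 |
| 0.8 | 0.15 | 0.165 | 0.07 |

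An uneven pattern (peak with AUC 0.9, infarction with MACE 0.6, lower elsewhere) gives 0.25 to 0.27 for seven tests.

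**Step 4. Rare binary outcomes.** The SAP switches to Fisher's exact test when an expected count is below five, and that test is conservative. With 270 per arm, the actual size of the chi-square/Fisher rule is about 0.011 at an assumed event rate of 1%, 0.039 at 2%, and close to 0.05 from 3% upward. For three continuous and four binary outcomes, taken as independent:

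- all four binary outcomes at 1%: 1 − 0.95³ × 0.989⁴ = 0.18
- all four at 2%: 1 − 0.95³ × 0.961⁴ = 0.27

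The 0.30 for independent tests falls, but stays well above the per-test level. The documents give no event rates for these outcomes.

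**The case against.** The strongest reply is that the plan separates one primary analysis from the secondary analyses, that unadjusted secondary outcomes are common practice, and that the 0.05 in the secondary section is a per-comparison threshold. All of that is true. The last part rules out a reading that is tempting here: that the plan sets a 5% family error rate and breaches it. The SAP makes no such promise. A reader might also infer that the trial's overall type I error is inflated. It is not, because the primary question is one outcome with its own test.

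A second reply concerns size. A reader might take the 23% at correlation 0.5 as the rate for this plan, or say that a false result is more likely than one in five. The documents support neither statement. The 23% needs an assumed common correlation of 0.5, and the seven-test figure falls below one in five at 0.7 and above. A false claim of benefit is about half as likely as a false result in either direction. For infarction, MACE and death alone, a false result favouring the intervention has a chance of about 0.07, 0.06 and 0.05 at correlations 0, 0.5 and 0.8. The statement about morbidity and mortality is conditional on the intervention being effective; it is not a claim rule tied to these tests.

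A third reply concerns scope. The SAP covers the primary publication, so the protocol's extra biomarkers and later follow-up should not be added to its seven comparisons. They are left out of the counts above, as is the repetition in intention-to-treat and per-protocol populations.

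These points limit the size. They leave the rule itself standing: unadjusted secondary outcomes are defensible when labelled exploratory, and this plan instead calls them significant at the full level.

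**Conclusion.** The point holds as a weakness in how secondary results may be claimed. Under no effect, the chance of at least one significant secondary result is about 15% to 30% for seven tests, or about 17% to 37% for nine if the troponin outcomes are tested within each assay stratum. A false result favouring the intervention has a chance of about 7% to 16% with seven tests. These ranges assume a common correlation from 0.8 down to 0 and tests of exact 5% size; they are somewhat lower if binary events are rare. No single figure within them can be taken from the documents.

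The primary test and its sample size stand, and no stated error rate is breached. What remains is that the plan's own wording would let an isolated secondary p-value below 0.05 be reported as a significant effect after a failed primary test. Correcting it is a cheap improvement.

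**What to change.** In the final SAP, replace the significance sentence under Secondary analyses with: 'Only the primary chi-square test supports a confirmatory claim. Secondary outcomes are exploratory; their p-values are nominal and will not be called statistically significant.' In the current protocol's Statistics section, limit the p < 0.05 sentence to the primary outcome.

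If the sponsor wants a confirmatory secondary claim, apply Holm's procedure at two-sided 0.05 to the seven listed outcomes, and only if the primary test is significant. Peak troponin and AUC should then supply one assay-stratified p-value each, so that the family is seven and not nine. Holm's first threshold would be 0.05/7 = 0.00714. Under no effect this gives a family error of 1 − (1 − 0.00714)^7 = 4.9% for independent tests and about 4.0% at correlation 0.5, before counting the gate on the primary.

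The cost is one or two sentences in each document. Patients, data collection and primary power are unchanged. The downside is that an isolated secondary p-value below 0.05 can no longer be reported as a significant effect.

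### Peak troponin and troponin AUC are stratified by assay, but the SAP names no test that combines the strata and no pooled effect

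*Combined protocol and SAP*

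**What the plan says.** For peak troponin, the final SAP's Secondary analyses specify: "Peak plasma troponin I within four days of surgery (stratified on cardiac troponin I and high-sensitive troponin I". Troponin AUC carries the same qualification, in the next item of that list. One sentence sets the tests for every continuous outcome: "Continuous outcomes will be analyzed with non-parametric (Wilcoxon two-sample test) or parametric statistics (unpaired t-test". Which of the two applies is to be settled by how the data are distributed and whether variances are equal, and log transformation is allowed if needed. The threshold is "Differences are considered significant if the two-sided p-value < 0.05".

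Results are to be given as follows: "Continuous outcomes will be expressed as mean (95% confidence interval) or median (inter-quartile range". These are summaries of each group, not a treatment effect pooled over assays.

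The strata are defined in the final protocol, under Plasma cardiac troponin I: "Siemens Healthcare Dimension Vista (Zealand University Hospital, Herlev Hospital), Abbott high-sensitive troponin I (Holstebro Hospital". The final protocol's Primary outcome section also sets different cut-offs, 45 ng/L for the conventional assay and 24 ng/L at Holstebro. The assay is therefore fixed by hospital.

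The only model in the SAP concerns the binary primary outcome: "To analyze the association between the intervention and the primary outcome, myocardial injury, we will do a univariate and multivariate logistic regression". In the protocol, the Statistics section adds no stratified method. The SAP's Summary of Changes records the decision to stratify without naming a method.

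**The concern.** Keeping the two assays apart is sound, because their raw values should not be pooled. What is missing is the step that brings the two strata back to one answer. A two-sample Wilcoxon test and an unpaired t-test each compare two groups and have no place for a stratum. An analyst who follows the text would most naturally run the chosen test once per assay and obtain two p-values for peak and two for AUC.

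The plan then gives no overall test and no combined estimate. It also does not say what to conclude if one assay shows a difference and the other does not. Whatever reading is adopted would be chosen after the results are known, and the power and false-positive rate depend on that choice.

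**Working it through.** **The plan's own figure.** The documents give no power for peak troponin or AUC. The only calculation is for the primary outcome: 15% versus 7%, 5% type I error, 80% power, 264 per arm. The two-sided formula without continuity correction gives 239 per arm, and with the correction 264. The stated number is reproduced and is not in dispute.

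**Inputs for the illustration**
- From the documents: two-sided 0.05 per comparison; 270 evaluable patients per arm; two assay strata.
- Assumed, because the documents do not give them: a Holstebro share of 20-40% (10-50% as a wider check), and the same standardised log-scale effect in both strata, sized so that one combined test has 80% power.

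**Step 1. Effect.** The combined test needs a non-centrality of 1.96 + 0.84 = 2.80. With 270 per arm this is a standardised effect of 2.80 × √(2/270) = 0.241.

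**Step 2. Power in one stratum.** For a stratum holding share s of the patients, power = Φ(2.80√s − 1.96).
- s = 0.2: 2.80 × 0.447 = 1.25, and Φ(−0.71) = 0.24.
- s = 0.8: 2.80 × 0.894 = 2.51, and Φ(0.55) = 0.71.

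**Step 3. The two strata together.** They contain different patients, so with stratum powers p1 and p2, P(at least one significant) = 1 − (1 − p1)(1 − p2) and P(both) = p1 × p2.

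| Holstebro share | Per arm, Vista / Holstebro | Vista alone | Holstebro alone | At least one | Both |
|---|---|---|---|---|---|
| 10% | 243 / 27 | 0.757 | 0.141 | 0.792 | 0.107 |
| 20% | 216 / 54 | 0.707 | 0.240 | 0.778 | 0.170 |
| 30% | 189 / 81 | 0.650 | 0.335 | 0.767 | 0.218 |
| 40% | 162 / 108 | 0.583 | 0.425 | 0.761 | 0.248 |
| 50% | 135 / 135 | 0.508 | 0.508 | 0.758 | 0.258 |

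**Step 4. False positives per outcome, by decision rule**
- Either stratum significant: 1 − 0.95² = 0.0975.
- Both strata significant: 0.05² = 0.0025.
- One stratified test: 0.05.

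**Step 5. Simulation check.** Log-normal data were simulated, 4,000 runs per setting, at Holstebro shares of 20-50%. With no effect, at least one of two separate Wilcoxon tests was significant in 9.0-10.6% of runs, and one van Elteren test in 4.4-5.8%. With the effect of 0.241, at least one separate test was significant in 73-75% of runs, and the van Elteren test in 77-78%.

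**The case against.** The strongest reply is that the sentence on tests is a general rule for all continuous outcomes, and that the words on stratification modify it for these two. Read that way, the plan could mean one Wilcoxon test stratified on assay, which is the remedy proposed here. This stands in part. A reader might infer that the SAP prescribes separate tests, and it never says so. But the test it names is the two-sample one, the t-test alternative has no stratified form without a model, and no pooled effect is specified on either reading. The gap remains, and the same edit closes it.

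A second objection also stands. A reader might infer that the plan suffers both a large loss of power and a near-doubled error rate. No single decision rule produces both. If either stratum suffices, power stays close to the combined test's 80% and the error rate is 9.75%. If both are required, power is about 17-25% at shares of 20-40%, but the error rate falls to 0.25%. The SAP adopts neither rule.

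A third inference would multiply the error over all four tests as if they were independent. Peak and AUC come from the same patients' samples, so that figure is not supported. Nor do the documents rank either outcome as the trial's principal continuous measure; they are two of seven listed secondary comparisons.

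**Conclusion.** The point holds as an unspecified combining step. For peak troponin and for AUC, the tests named do not yield one answer across the two assays, and nothing else in the protocol or SAP supplies it.

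The certain part is the missing overall test, pooled effect and rule for discordant results. The size is illustrative. At a Holstebro share of 20-40%, and with a common effect that gives one combined test 80% power, the Vista stratum alone has about 58-71% power and the Holstebro stratum about 24-43%. Reading either stratum as positive gives about 76-78% (76-79% over shares of 10-50%), at a 9.75% false-positive chance per outcome. The power figures depend on the assumed share and effect. The 9.75% depends only on two independent tests at 0.05 and that reading.

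Only secondary outcomes are concerned. It would be wrong to infer that the trial's main result is at risk, since the primary chi-square test and the sample size do not rest on this step. The change should be made, but the trial does not stand or fall on it.

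**What to change.** In the final SAP's Secondary analyses, name one pre-specified primary analysis for each of the two outcomes:

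- **Test.** The assay-stratified Wilcoxon (van Elteren) test, whatever the distribution of the data, giving one p-value for peak and one for AUC.
- **Estimate.** A ratio of geometric means with 95% confidence interval, from a linear model on log troponin with treatment and assay terms. This supplies the pooled effect and is not a second route to significance.
- **By assay.** Medians and inter-quartile ranges shown descriptively, without separate claims of significance. State that the high-sensitive assay coincides with the Holstebro site, so a difference between strata cannot be attributed to assay rather than hospital.

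The cost is a few sentences in the SAP. No new data are needed, and the test is available in SAS, one of the packages that the protocol names. The downside is that the pooled ratio assumes similar proportional effects on both assays. That assumption should be stated next to the estimate.
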